6.3 Study Discontinuation and Patient Withdrawal Criteria

While patients will be encouraged to continue on study for safety follow-up, patients **MUST** be discontinued from receiving further study agent for the following reasons:

[figure not shown]
- Symptomatic deterioration attributed to disease progression as determined by the investigator after integrated assessment of radiographic data, biopsy results, and clinical status (see Figure 5)
- Intolerable toxicity related to study treatment, including development of an irAE determined by the investigator and Medical Monitor to be unacceptable given the individual patient's potential response to therapy and severity of the event
- Any medical condition that may jeopardize the patient's safety if he or she continues on study treatment
- Use of another non-protocol anti-cancer therapy
- Withdrawal of informed consent (patient's decision to withdraw for any reason).
- Pregnancy (**NOTE:** All FCBPs should be instructed to contact the Investigator immediately if they suspect they might be pregnant at any time during study participation.)

- Termination of the study by Sponsor for safety or other reasons.
- Imprisonment or the compulsory detention for treatment of either a psychiatric or physical illness (e.g., infectious disease).
- Any clinical AE, laboratory abnormality or intercurrent illness that, in the opinion of the Investigator, indicates that continued dosing on the study is not in the best interest of the patient.
- Patients who cannot tolerate CMB305, atezolizumab, or outpatient study procedures.
- PD by irRC criteria.²⁷

As long as they are receiving atezolizumab and/or combination treatment, patients will be permitted to continue study treatment if the RECIST v1.1 criteria for PD are met provided they meet all of the following criteria (Figure 5):

- Evidence of clinical benefit as assessed by the Investigator
- Absence of symptoms and signs (including worsening of laboratory values; e.g., new or worsening hypercalcemia) indicating unequivocal progression of disease
- No decline in ECOG performance status that can be attributed to disease progression
- Absence of tumor growth at critical anatomical sites (e.g., leptomeningeal disease) that cannot be managed by protocol-allowed medical interventions
- Patients for whom approved therapies exist must provide written consent to acknowledge deferring these treatment options in favor of continuing study treatment at the time of initial apparent progression.

Figure 5 Conditions for Continuing Atezolizumab Alone or in Combination in the Presence of Increased Radiographic Tumor Size

ECOG PS=Eastern Cooperative Oncology Group performance status; ICF=Informed Consent Form; RECIST=Response Evaluation Criteria in Solid Tumors v1.1.

Unless consent is withdrawn and the patient is unwilling to continue with safety follow-up, the patient is lost to follow-up, or the study is terminated, all efforts should be made to continue safety monitoring of all patients who received CMB305 and/or atezolizumab. A safety evaluation should always be done at the last site visit if feasible.

Patients who withdraw from the study prior to the EOS should be followed for new AEs for at least 30 days after their last dose of CMB305 and/or atezolizumab. If the patient withdraws

prematurely and is unwilling to continue safety follow-up, any subsequent SAE that may be causally related to CMB305 or atezolizumab that comes to the attention of the site staff should be reported to IMDZ.

Patients in whom radiographic disease progression is confirmed at a subsequent tumor assessment may be considered for continued study treatment at the discretion of the Investigator provided they meet the criteria above.

Patients who have permanently discontinued atezolizumab must discontinue study treatment if they meet criteria for disease progression per RECIST/irRC. The primary reason for study treatment discontinuation should be documented on the appropriate electronic Case Report Form (eCRF). Patients who prematurely discontinue study treatment will not be replaced.

Patients who discontinue study treatment for reasons other than disease progression (e.g., toxicity) should continue to undergo scheduled tumor assessments at the same frequency as would have been followed if the patient had remained on study drug until the patient dies, experiences disease progression, withdraws consent, starts a new anti-cancer therapy, or until the study closes, whichever occurs first.

On-study radiotherapy and surgeries should continue to be recorded until documented radiographic progression, even if progression occurs after study treatment discontinuation. Non-protocol systemic anti-cancer therapies administered before documented radiographic progression should be recorded as concomitant medications.

The primary reason for study treatment discontinuation should be documented on the appropriate eCRF. Patients who discontinue study treatment prematurely will not be replaced.

The Sponsor has the right to terminate this study at any time. Reasons for terminating the study may include, but are not limited to, the following:

- The incidence or severity of adverse events in this or other studies indicates a potential health hazard to patients.
- Patient enrollment is unsatisfactory.

The Sponsor will notify the investigator if the Sponsor decides to discontinue the study.

The Sponsor has the right to close a site at any time. Reasons for closing a site may include, but are not limited to, the following:

- Excessively slow recruitment
- Poor protocol adherence

- Inaccurate or incomplete data recording
- Non-compliance with the International Conference on Harmonisation (ICH) guideline for Good Clinical Practice (GCP) No study activity (i.e., all patients have completed and all obligations have been fulfilled)

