- b. Patients will be followed with visits every 3 weeks (± 4 days) for 2 years (from Day 0) for until progression. Tumor size will be assessed every 6 weeks for the first year, then every 12 weeks until progression. Patients will then have no further staging procedures. Tumor biopsies will be obtained at 6 months or longer for patients with treatment response. Tumor biopsies will also be obtained at time of progression.
- c. Informed consent and HIPAA authorization must be signed before any screening study-related procedures are initiated. Three informed consents will be used: one to screen tumor sample for NY-ESO-1, one to engage in the study protocol, and an agreement to continue in the study and obtain peripheral blood samples and biopsies if the patient meets the criteria for progressive disease but wishes to remain on study.
- d. Documentation of NY-ESO-1 expression in prior tumor samples may have been collected from any procedure performed before baseline activities. There is no time limit for use of the results from the IMDZ-approved central lab.
- e. Vital sign measurements include temperature, pulse, respiratory rate, and resting systolic and diastolic blood pressure. On the day of each dosing, vital signs will be obtained pre-dosing and 30 minutes after dosing. For the first atezolizumab infusion, the patient's vital signs (HR, respiratory rate, BP, and temperature) should be measured within 15 minutes of the infusion, during the 60-minute infusion (every 15 \pm 5 minutes), and 30 minutes after the infusion. For subsequent infusions, vital signs do not need to be obtained during the infusion if the prior infusion was tolerated without symptoms.
- f. Once the baseline physical exam has been conducted, a simple symptom-directed physical exam should be performed for all subsequent visits. Height and weight will be collected at Day 0 only.
- g. Imaging will be performed by CT scan as defined by RECIST/irRC at screening and every 6 weeks after first study injection for the first year, then every 12 weeks for tumor staging until disease progression and includes a confirmatory scan performed at least 4 weeks later. Magnetic Resonance Imaging (MRI), bone scans, or PET/CT at baseline or subsequent visits will be performed only if clinically indicated.

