5.0 INVESTIGATIONAL PLAN

5.1 Overall Trial Design and Plan

This is a randomized, open-label, Phase 2 trial of CMB305, a treatment regimen of LV305 and G305, in combination with atezolizumab or with atezolizumab alone in patients with sarcoma who have had an inadequate response, relapse, and/or unacceptable toxicity with one or more prior systemic, surgical, or radiation cancer therapies. Approximately 80 patients at up to 20 sites in the United States (US) and Canada will be enrolled.

All patients will have tumor samples screened for expression of NY-ESO-1 to determine eligibility. Archival tumor specimens will be obtained from patients to determine PD-L1 molecular status. Patients will be randomized in a 1:1 allocation ratio to receive CMB305 in combination with atezolizumab or atezolizumab alone. Randomization will be 1:1 and stratified by disease type. For the combined treatment arm, the trial will be conducted in 4 phases: Treatment Phase (study Days 0 to 84), Booster Phase (post Day 84 to 1 year post Day 0), Maintenance Phase (from 1 year to 2 years post Day 0), and Survival Follow-up Phase (quarterly thereafter). For the control arm, the trial will be conducted in 3 phases: Treatment Phase (study Days 0 to 84), Maintenance Phase (post Day 84 to 2 years post Day 0), and Survival Follow-up Phase (quarterly thereafter).

CMB305 treatment will consist of 2 doses of LV305 administered on Days 0 and 14, followed every 2 weeks with alternating doses of G305 and LV305. In total, 4 doses of LV305 and 3 doses of G305 will be administered over a period of 3 months. Patients will receive CMB305 according to doses and treatment schedules determined in previous studies. LV305 will be administered intradermally (ID) at a dose of 1×10^{10} vector genomes (vg) and G305 will be administered intramuscularly (IM) at a dose of GLA-SE (5 µg) mixed with 250 µg of NY-ESO-1 protein. Atezolizumab will be given intravenously (IV) every 3 weeks and may be continued up to 2 years until toxicity develops or confirmed progression. A G305 booster dose will be given every 6 weeks in the first year until disease progression (to coincide with the staging follow-up visits). The control arm (atezolizumab treatment alone) will return to the clinic for dosing every 3 weeks until progression or toxicity develops.

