Appendix C RECIST and Immune-Related Response Criteria

For this study, both RECIST v1.1 and RECIST-based irRC data will be collected but only irRC will be used to determine disease progression. Full RECIST definitions are included in the Study Reference Manual.

The irRC was originally developed using the World Health Organization (WHO) tumor response measurement criteria where bidimensional measurements were used to define tumor burden.²⁷ In solid cancers, RECIST is now more commonly used. RECIST uses the sum of the longest unidimensional measurement of tumor lesions as the basis of its criteria. Many have now adopted a modified RECIST-based irRC as the criteria used to measure the effect of immunotherapeutic approaches in solid cancers (see comparisons below). Nishino, *et al* prospectively examined the impact of using bidimensional vs. unidimensional measurements.³⁷ They concluded that irRC using the unidimensional measurements provided highly concordant response assessment compared with the bidimensional irRC, with less measurement variability and recommended the use of unidimensional irRC to assess response to immunotherapy in solid tumors.

Appendix Table 1 Summary of Measurement and Response Assessment Approaches for Bidimensional and Unidimensional Assessment Based on irRC

	Bidimensional assessment (the original irRC)	Unidimensional assessment
Measurable lesions	≥5 x 5 mm ² by bidimensional measurements	≥10 mm in the longest diameter
Measurement of each lesion	The longest diameter x the longest perpendicular diameter (cm ²)	The longest diameter (cm)
The sum of the measurements	The sum of the bidimensional measurements of all target lesions and new lesions if any	The sum of the longest diameters of all target lesions and new lesions if any
Response assessment	PD: ≥25% increase from the nadir PR: ≥50% decrease from baseline CR: Disappearance of all lesions	PD: ≥20% increase from the nadir PR: ≥30% decrease from baseline CR: Disappearance of all lesions
New lesions	The presence of new lesion(s) does not define progression. The measurements of the new lesion(s) are included in the sum of the measurements.	

Confirmation Confirmation by 2 consecutive observations not less than 4 weeks apart was required for CR, PR, PD

As published in Nishino et al.³⁷

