- Immune-related Progressive Disease (irPD): increase in tumor burden $\geq 20\%$ relative to nadir (minimum recorded tumor burden) and confirmation by a repeat, consecutive assessment no less than 4 weeks from the date first documented

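### For a patient with confirmed irRC progression who meets the continuation conditions, Protocol Section 6.3 says both that study agent must stop and that it may continue

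*Protocol*

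**What the plan says.** **The stop rule.** Section 6.3 opens with an obligation, in capitals, that patients must "be discontinued from receiving further study agent for the following reasons". One listed reason is "PD by irRC criteria". It carries no exception and no cross-reference to the paragraphs that follow.

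**The definition.** Appendix D defines irRC progression as an increase in tumor burden of at least 20% from nadir with "confirmation by a repeat, consecutive assessment no less than 4 weeks from the date first documented". Appendix C adds that "only irRC will be used to determine disease progression".

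**The permissions to continue.** Section 6.3 contains two:

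- Patients on atezolizumab or the combination are "permitted to continue study treatment if the RECIST v1.1 criteria for PD are met", subject to five conditions: investigator-assessed benefit, no symptoms or signs of unequivocal progression, no ECOG decline due to progression, no unmanageable growth at critical sites, and written consent where approved therapies exist.
- Further on: "Patients in whom radiographic disease progression is confirmed at a subsequent tumor assessment may be considered for continued study treatment", at the investigator's discretion and under the same conditions.

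**Elsewhere.** Section 5.1 says atezolizumab "may be continued up to 2 years until toxicity develops or confirmed progression". Footnote b of Tables 1 and 2 follows the scan schedule to progression and then says: "Patients will then have no further staging procedures".

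**The concern.** A mandatory stopping rule for investigational agents should give one answer for any patient. Here the answer depends on which paragraph of Section 6.3 a site reads, and the choice is made unblinded.

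Four things can vary with that choice:

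- **Exposure**, and with it the treatment-emergent adverse event window, which SAP Section 7.8.1 runs to 30 days after the last dose.
- **Time to next treatment**, a secondary endpoint. Section 6.3 makes another anti-cancer therapy a reason to stop study agent, and the consent condition describes putting off approved options in order to stay on study treatment.
- **The post-progression treatment behind OS**, a primary endpoint.
- **Protocol deviations.** SAP Section 7.4 has the study team define major deviations that exclude patients from the efficacy evaluable set. Whether dosing after irRC progression is a deviation cannot be decided from this text.

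**Working it through.** The plan states no figure on this point, so the check is a comparison of texts.

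**Step 1: what the stop rule covers.** Under Appendix D an unconfirmed increase is not yet irRC progression. The stop rule therefore applies to progression that has already been confirmed.

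**Step 2: the first permission.** RECIST v1.1 progression can occur without irRC progression. Appendix D records any new lesion as progression under RECIST v1.1. Under irRC a measurable new lesion is added to the tumor burden, and a non-measurable one does not define progression. A patient with a new lesion and a total burden less than 20% above nadir can continue under the first permission without meeting the stop rule. These two provisions are compatible.

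**Step 3: the second permission.** This sentence concerns radiographic progression confirmed at a later assessment. It is not limited to RECIST-only progression. Confirmation is the feature that the irRC modification adds, and Section 5.7 expressly ties confirmed radiographic progression to irRC.

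**Step 4: one patient under both rules.** Take a patient on atezolizumab whose tumor burden is at least 20% above nadir, confirmed at least 4 weeks later, and who meets all five conditions.

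| Provision of Section 6.3 | Does it apply? | Result |
|---|---|---|
| Mandatory stop for irRC progression | Yes, the increase is confirmed | Must stop |
| Permission after confirmed radiographic progression | Yes, confirmed and conditions met | May continue |

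Neither provision says which prevails. A further sentence in Section 6.3 requires patients permanently off atezolizumab to stop study treatment at progression per RECIST or irRC. For irRC progression that sentence would be redundant if such progression always required stopping.

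**Step 5: whether the rest of the protocol settles it.** It points both ways.

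- Until confirmed progression: Synopsis (Study Design), Figure 1 note, Section 5.1.
- Until disease progression, not qualified as confirmed: Section 7.2.
- Continuation in the absence of symptomatic progression, referring to Section 6.3: Synopsis (Study Design, paragraph on dosing interruptions).
- Atezolizumab up to 2 years, with toxicity the only stated end: Section 5.2.
- A separate agreement for patients who meet progression criteria and wish to stay on study: footnote c of Tables 1 and 2.

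**Step 6: scans after progression.** Footnote b ends staging at progression, so under it a patient who continues has no scheduled scans. Section 8.2.3.1 sets booster-phase visits, with CT staging among the assessments, to 1 year or progression, whichever is later. Read literally, that could extend staging past progression, so it also needs reconciling.

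**Step 7: effect on PFS.** Protocol Section 10.2.2.4.1 and SAP Section 5.1.1.1 date confirmed progression to the first scan that showed the increase. Dosing after confirmation does not change that date.

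**The case against.** The strongest reply is that treatment beyond initial progression is deliberate. The Synopsis sends the reader to Section 6.3, footnote c provides a consent for it, and the confirmed-progression sentence relies on conditions set out under the RECIST v1.1 permission. On that reading, confirmed means confirmed RECIST v1.1 progression that is not irRC progression, and the rules never meet. This narrows the group affected, and it is right about the first permission. It does not remove the conflict, because the sentence carries no such limit and Section 5.7 uses the same idea for irRC progression.

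Figure 5, which Section 6.3 cites for both the symptomatic stop and the continuation conditions, is not shown in the text available here. It may put the rules in order, but the two sentences conflict as written.

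It is also fair that the consequences are bounded. The primary OS and PFS analyses are Kaplan-Meier summaries by arm, between-arm comparisons are exploratory, and p values are nominal. Symptomatic deterioration, intolerable toxicity and investigator-judged adverse events remain independent mandatory stops. The documents show no difference between arms in how the rule would be applied.

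**Conclusion.** The contradiction is real but confined to patients on atezolizumab with confirmed irRC progression who meet every continuation condition. It rests on the unlimited wording of the confirmed-progression sentence and on the irRC definition in Appendix D.

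Its size cannot be derived from the documents. A reader might apply the planning 6-month progression-free rates of 25% and 45%, one to each arm, and infer that most of the trial is affected: 40 × (1 − 0.25) + 40 × (1 − 0.45) = 30 + 22 = 52 of 80. The documents do not support this, for two reasons:

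- The rates are the unacceptable and acceptable values for each arm's Simon design, not one forecast per arm. The same rate in both arms gives 80 × 0.55 = 44 or 80 × 0.75 = 60.
- Any such count is of all PFS events by month 6. It includes deaths and patients who could not meet the continuation conditions, and no document says what fraction would qualify.

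A reader might also infer that PFS is biased. Step 7 shows that its dates do not move. What remains is possible site-to-site variation in exposure, the adverse event window, time to next treatment and the treatment behind OS, together with a stopping rule that has two answers.

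**What to change.** Reconcile the mandatory-stop item and the confirmed-progression paragraph in Section 6.3 so that one rule applies after confirmed irRC progression. The clinical team chooses the rule; this review takes no position on it.

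Then bring the other places into line: the Synopsis (both statements), the Figure 1 note, Sections 5.1, 5.2 and 7.2, footnotes b and c of Tables 1 and 2, and Figure 5. SAP Section 3.1 and its copies of the schedules repeat some of this text and should follow. Make the staging schedule match the chosen rule, including Section 8.2.3.1. State whether dosing contrary to the rule is a major deviation under SAP Section 7.4.

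The cost is a wording amendment. The reconciliation itself needs no new data; whether any scans are added depends on the rule chosen.

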7.0 STUDY TREATMENTS

7.1 Investigational Drugs

The investigational drug is CMB305, a prime-boost combinatorial regimen comprised of 2 different active immunotherapy agents, LV305 and G305 administered sequentially to prime and boost the immune system in order to induce a strong CD8 T cell response against tumor cells resulting in tumor regression. The prime-boost therapy is being tested in combination with investigational anti-PD-L1 CPI atezolizumab.

7.1.1 LV305

LV305 is the product name for ZVex2.0 encoding the NY-ESO-1 CT antigen. It is a modified LV-based on IMDZ's ZVex™ platform designed to target production of NY-ESO-1 in DCs via a modified Sindbis virus glycoprotein (SINVar1). It has been engineered to enhance safety such that it is dendritic cell-tropic, replication-incompetent, and integration-deficient.⁷ LV305 contains 1×10^{10} vg/mL in Tris buffer (pH 7.5) containing 5% sucrose and L-arginine as outlined in Table 3.

Table 3 LV305 Drug Product Components

Component	Amount per mL	Amount per vial	Function
LV305	1×10^{10} vg/mL	1.4×10^{10} vg/mL	Active component
L-arginine	8.71 mg/mL	12.2 mg/vial	Excipient
Tris buffer	6.06 mg/mL	8.48 mg/vial	Excipient
Sucrose	50 mg/mL	70 mg/vial	Excipient

vg = viral genomes.

Source: CMB305 Investigator Brochure⁶

For further details regarding LV305, its properties, and formulation, please consult the CMB305 IB.⁶

7.1.1.1 Investigational Drug Packaging and Labeling

The LV305 investigational Drug Product will be supplied in a one-vial configuration where a 1 mL injection volume will correspond to the total dose. Each vial contains 1.4 mL of formulated LV305 (1×10^{10} vg/mL) packaged in a 2 mL vial.

7.1.1.2 Storage and Disposition of the Investigational Drug Products

LV305 must be stored at -60°C (or colder). Upon completion of the study, all remaining materials must be returned to IMDZ unless otherwise instructed.

7.1.1.3 Dose Preparation for Administration to the Patient

The Drug Product will be used as provided in the vial. Instructions detailing thawing of the vial and preparation of dosing syringes will be provided in the Pharmacy Manual.

One (1) mL of the thawed product will be administered as 8×125 μL ID injections (2 injections over each deltoid and 2 over each of the quadriceps) on Days 0, 14, 42, and 70 as outlined in the Schedule of Events (Table 1) and the Pharmacy Manual. Each ID injection should be at least 3 cm from the neighboring injection.

